1.0 SPECIFIC STUDY AIMS

The purpose of this study is to evaluate the safety of tourniquet use and subsequent resolution of swelling in patients with prior axillary lymph node dissection. We hypothesize that a tourniquet placed for a short period of time at low pressure will cause edema without complication in both arms ipsilateral and contralateral to the side of axillary lymph node dissection in patients status post prior axillary lymph node dissection for cancer.

2.0 BACKGROUND AND RATIONALE

The safety of elective hand surgery in breast cancer patients following ipsilateral axillary lymph node dissection (ALND) is controversial due to concerns of developing upper extremity lymphedema. Prior authors have discussed concern for invasive and non-invasive manipulation of the extremity, including blood pressure measurements, injections, and intravenous access¹⁻², although the evidence for these factors in the onset or progression of lymphedema is limited. However, this is controversial in the oncology literature despite being widely accepted in the hand surgery literature³⁻⁵. Patients are commonly dissuaded from routine elective hand surgery for coexistent pathology⁶. Prior studies have demonstrated no to minimal risk of developing lymphedema acutely or late following hand surgery after prior ALND⁶⁻⁹. Furthermore, no evidence is available to demonstrate a relationship between tourniquet use and lymphedema⁶⁻⁹, and existing literature supports the use of an upper arm tourniquet in patients with prior breast cancer treatment of ALND. The acute effect of swelling in the setting of a tourniquet and the time required for swelling reduction for this population, however, remains unknown.

A pilot study has been completed to evaluate tourniquet use in healthy volunteers and the chosen pressure of 40 mmHg was identified as leading to repeatable swelling without acute or chronic abnormalities. Higher pressures (250, 120, 100 and 80 mmHg) lead to a similar 30-40 mL increase in volume in a healthy volunteer, although transient nerve palsy, pain and petechiae were identified at the higher pressure. No complications were identified in 8 healthy volunteers at 40 mmHg over 25 minutes. The increase in hand volume was less than 30 mL at 30 mmHg or less. Therefore, 40 mmHg most reliably recreates temporary edema formation, while limiting unnecessary or prolonged tourniquet use. Pilot study results further found that both the on head and brace limb postures markedly and significantly decreased swelling greater than the sling posture ($p < .001$).

The purpose of the proposed study is to evaluate the acute impact of swelling caused by low-pressure tourniquet use in the setting of ipsilateral ALND and the change in swelling reduction following tourniquet use in two limb postures, comparing the arms ipsilateral and contralateral to the side of ALND. We hypothesized that tourniquets may be safely applied to patients with prior ALND in either their ipsilateral or contralateral arm. We further hypothesized that patients who have had prior ipsilateral ALND would have an equivalent proportion of upper extremity edema and see improved resolution with increased elevation. Understanding the effect of tourniquet use and its safe practice will aid in the surgical management of patients with prior axillary lymph node dissection.

3.0 STUDY ENROLLMENT AND PARTICIPANT ELIGIBILITY

All patients over the age of 18 who have previously undergone axillary lymph node dissection will be invited to participate in the study. Participants will be identified via chart review of patients with prior ALND.

3.1 Study Enrollment

Recruitment will occur via telephone or in-person encounters based on retrospective review for patients meeting the above inclusion criteria. Advertising for this study is not planned. Participants will be screened based on the above criteria and the exclusion criteria in part 3.2 below. Participants who fail inclusion on screening will be excluded.

The study coordinator or the above study members will consent the patient prior to involvement. In a closed and quiet room, the potential research subject will be able to ask any questions regarding the study and its procedures. No recruitment materials will be provided at the time of consent. Participants may withdraw consent at any time.

3.2 Participant Criteria

All patients over the age of 18 who have previously undergone axillary lymph node dissection will be invited to participate in the study. Patients will serve as their own internal control, using both arms which are ipsilateral and contralateral to the side of ALND. Patients will be excluded who have new-onset lymphedema of the involved limb, infection including cellulitis, or trauma or planned axillary surgery within 6 months of participation.

3.3 Enrollment

Given the variability in our pilot study, we determined by power analysis that we would need to recruit 45 participants (for a total of 90 arms) for the current study for evaluation of relative edema and its reduction following tourniquet use. We expect the study to begin upon approval, 4/2017 and conclude after recruitment in approximately 6-12 months.

4.0 MATERIAL AND METHODS

Study participants will be seated and patients' arms ipsilateral to prior axillary lymph node dissection will be elevated with the hand above the level of the ipsilateral shoulder for 15 minutes. This is to ensure an accurate baseline in all participants. Hand volume will be measured by aqueous volumeter to the level of the proximal wrist crease for a baseline. A tourniquet will then be placed on each study participant's upper arm, again ipsilateral to prior axillary lymph node dissection. This will be inflated to 40 mmHg for 25 minutes, after which hand volume will be again measured as described above. The limb will then be placed in an elevated position at shoulder height or in a sling at the waist, and hand edema will again be measured. The process will be repeated for each limb position after a 15-minute break time. The two limb positions are "sling," with the hand at the level of the waist, and "elevated" with the hand at the level of the shoulder. This will be repeated for the contralateral, healthy arm which will serve as an internal control.

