5.0 STATISTICAL CONSIDERATIONS

We will evaluate the data per recommendations of our statistician by categorical and continuous statistical testing, as applicable. For the primary outcomes of percentage change in hand volume from baseline after tourniquet application, and secondary outcome of residual volume as a percentage of baseline following limb positioning, we will compare the healthy contralateral arm versus the arm status post ALND. Paired t-tests will be used to compare measures averaged to produce a single pre-tourniquet hand volume and a single post-tourniquet hand volume. The differences will again be compared between patients' arms ipsilateral and contralateral to the side of ALND. Linear mixed effects model will also be fitted to account for the correlations between measurements on the same subject and history of ALND, arm position after tourniquet use, and patient-specific risk factors. This specific issue power analysis is further discussed below (5.3).

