5.1 Outcome Measurements

Study participants will be evaluated prior to and following the above process.

Data collection:

- A. Demographic will be recorded: Age, sex, height, weight, BMI, comorbidities, number of lymph nodes excised in ALND, and presence of lymphedema
- B. Procedural measures: hand volume and percent change

Primary outcome: percentage change in hand volume from baseline after tourniquet application

Secondary outcome: residual volume as a percentage of baseline following limb positioning after tourniquet use

- C. Tourniquet complications: unresolved edema (i.e. persistent swelling lasting greater than the 30 minute evaluation period), petechiae (i.e. pinpoint skin redness or purple color caused by a minor bleed from broken capillary blood vessels), pain, paresthesias (tingling sensation), palsy (neurologic change related to peripheral nerve compression), by direct visualization and neurologic evaluation by a medical provider at the time of tourniquet use

Acute or delayed symptoms related to tourniquet use will be assessed and managed with routine care. Participants may contact the study staff at any time regarding delayed complication.

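### The order of the two limb positions within an arm is not specified or balanced and the model has no run term, so the elevated-versus-sling contrast can be confounded with run order

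*Combined protocol and SAP*

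**What the plan says.** Section 4.0 describes one run as follows. The arm is "elevated with the hand above the level of the ipsilateral shoulder for 15 minutes", and a baseline hand volume is taken. The cuff goes on ("This will be inflated to 40 mmHg for 25 minutes") and the volume is measured again. The limb is then positioned and measured a third time. The positioning step reads "The limb will then be placed in an elevated position at shoulder height or in a sling at the waist", and a little later "The process will be repeated for each limb position after a 15-minute break time". Each arm therefore does both positions in two successive runs, which is a two-period crossover of posture. The other arm comes next: "This will be repeated for the contralateral, healthy arm which will serve as an internal control".

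No section says which position comes first, who sets the order, or whether it is randomised or balanced. None gives the time spent in a position or requires the volume to be back at baseline before the cuff is inflated again.

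Section 2.0 hypothesises that patients will "see improved resolution with increased elevation". It also says that how long swelling takes to go down in this population is not known, and that two pilot postures reduced swelling more than the sling did (p < .001). Section 5.0 refers to "measures averaged to produce a single pre-tourniquet hand volume and a single post-tourniquet hand volume", which implies more than one baseline per arm. Its mixed model names within-subject correlation, ALND history, arm position and patient risk factors. Section 5.1 makes residual volume after positioning the secondary outcome. Section 5.3 leaves that outcome out of the power calculation.

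**The concern.** In a two-period crossover, the treatment contrast is free of period effects only if the order is balanced, or if order varies and period is modelled. Neither is provided for here. A run effect could come from swelling left over from run 1, or simply from the hand having been through the cuff once already.

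Washout cannot be taken for granted, because Section 2.0 itself says the time course is unknown. The pilot difference between postures also makes it plausible that the amount left over depends on which posture came first.

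What is at stake is the elevation hypothesis. If one order is used throughout, run and position coincide exactly. A run term added at analysis could not then be estimated, so the problem has to be prevented in the schedule.

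**Working it through.** The documents give no figure for the posture contrast, so there is none to reproduce. The power figures in Section 5.3 concern the primary arm comparison and contain no posture term.

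**Inputs from the documents**
- Rise after the cuff: R = 9.1 points (pilot median in normal controls, Section 5.3).
- Break between runs: 15 minutes (Section 4.0).

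**Assumptions (not in the documents)**
- Share of swelling left at the end of a position: 0.20 elevated, 0.50 sling.
- Half of that is left after the break.
- The second cuff adds another 9.1 points, clearance is proportional, and small changes in the denominator are ignored.

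**Step 1: swelling K present at the start of run 2**
- Elevated first: 0.20 × 9.1 × 0.5 = 0.91 points.
- Sling first: 0.50 × 9.1 × 0.5 = 2.275 points.

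This is not yet bias. Residual volume is measured after the second position, by which time part of K has cleared.

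**Step 2: shift in the run-2 residual**

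On the run-1 baseline the shift is (share left) × K. On a fresh run-2 baseline it is (share left) × K − K.

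| Order | Run-2 position | Run-1 baseline | Fresh run-2 baseline |
|---|---|---|---|
| Elevated first | sling | 0.50 × 0.91 = +0.455 | 0.455 − 0.91 = −0.455 |
| Sling first | elevated | 0.20 × 2.275 = +0.455 | 0.455 − 2.275 = −1.82 |

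A baseline averaged over both runs gives the same contrast as the run-1 baseline, because a common reference cancels from the difference. Averaging therefore does not remove carryover.

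**Step 3: bias in (elevated − sling)**

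Let f be the share done elevated first, c_s the run-2 shift after sling, and c_e the run-2 shift after elevated. Bias = (1 − f) × c_s − f × c_e. If both shifts equal p, this is p × (1 − 2f).

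The contrast without carryover, under the same assumptions, is 0.20 × 9.1 − 0.50 × 9.1 = 1.82 − 4.55 = −2.73 points.

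| Order used | Run-1 baseline | Fresh run-2 baseline |
|---|---|---|
| All elevated first (f = 1) | −0.455 | +0.455 |
| All sling first (f = 0) | +0.455 | −1.82 |
| Balanced (f = 0.5) | (0.455 − 0.455)/2 = 0 | (−1.82 + 0.455)/2 = −0.68 |

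A negative bias flatters elevation and a positive one understates it. The sign depends on both the order and the baseline.

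**Step 4: range**
- Full washout: K = 0 and every entry is zero.
- If the 15-minute elevation is repeated and clears another half, K is 0.455 or 1.1375. The shifts become +0.23 on the run-1 baseline, and −0.23 (elevated first) or −0.91 (sling first) on a fresh one.

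**The case against.** Four stronger readings are tempting, and the documents do not support them.

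- A reader might infer that staff choose the order. Section 4.0 does not say so; it is silent on who sets it.
- A reader might infer that the posture contrast is confounded as a matter of fact. That needs both an unbalanced order in practice and incomplete washout, and the documents establish neither.
- A reader might set the 15-minute break against Section 5.1's definition of unresolved edema, "persistent swelling lasting greater than the 30 minute evaluation period", and conclude that the break is too short. But the break starts after the position and its measurement, not at cuff release. The definition also treats swelling beyond 30 minutes as a complication, which suggests it is normally expected to have gone by then. In addition, the repeated process may include the preparatory elevation and a new baseline, which the averaging in Section 5.0 supports. On that reading at least 15 + 15 = 30 minutes separate the end of the first position from re-inflation.
- A reader might compare 0.91 to 2.275 points of carried-in swelling with the trial's 1-point margin. That is swelling at the start of run 2, not bias in residual volume, and Section 5.3 sets the margin for the primary arm comparison only.

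It is also fair to say that the secondary comparison in Section 5.0 is between arms. A posture order common to both arms largely cancels there, and repeating the procedure on the other arm most naturally means repeating it unchanged.

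Finally, balancing does not cure carryover that differs by posture: half the difference, (c_s − c_e)/2, remains. All of this narrows the point. What stands is that the order is unspecified, a return to baseline is not required, and the model has no run term.

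**Conclusion.** The point holds as a conditional weakness in a secondary question. If one order predominates and run-1 swelling has not fully cleared, the elevated-versus-sling contrast can be confounded with run order.

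The size is unknown. Bias is zero with full washout, and a common run effect gives zero bias under balanced order. With one fixed order, it equals in size the run-2 minus run-1 shift in residual volume. Under the fractions assumed above, that is about 0.5 points on the run-1 baseline, or about 0.5 to 1.8 points on a fresh run-2 baseline, against an assumed true contrast of 2.73 points. The documents supply none of those fractions.

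The stated power for the primary endpoint is untouched. The ipsilateral-contralateral comparison of residual volume is exposed to posture order only if that order differs between a patient's two arms. The change is worth making because it is cheap and because a single fixed order could not be repaired in the analysis.

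**What to change.** In Section 4.0:
- randomise posture order 1:1 per patient (sling first or elevated first) from a prepared list;
- use the same order in both of that patient's arms;
- state that the 15-minute elevation and the baseline measurement are repeated before run 2.

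In Section 5.0, add run (1 or 2) as a fixed term in the mixed model for residual volume, and say which baseline the residual is a percentage of.

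The cost is a short list, a few sentences and one degree of freedom, with no extra patients. If the elevation and baseline are not already meant to be repeated, each arm's session lengthens by that step.

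The limit should be stated openly: this removes a run effect common to both postures but leaves half of any difference in carryover between them. The repeated baseline lets the analysts check for that, by comparing run-2 with run-1 baselines according to which posture came first.

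### The plan describes the ALND arm first and the control arm second, without balancing arm order or including it in any analysis, so any order effect enters the primary ALND difference

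*Combined protocol and SAP*

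**What the plan says.** Section 4.0 gives the sequence in a single paragraph. It begins with patients' "arms ipsilateral to prior axillary lymph node dissection will be elevated with the hand above the level of the ipsilateral shoulder for 15 minutes", followed by the baseline volume. The cuff then goes on the upper arm, "again ipsilateral to prior axillary lymph node dissection". Two limb positions follow: "The process will be repeated for each limb position after a 15-minute break time". Only after that does the text turn to the other side: "This will be repeated for the contralateral, healthy arm which will serve as an internal control". The 15-minute break is stated for limb positions; no interval between arms is given.

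The primary outcome is percent change in hand volume after the cuff, relative to baseline, compared between a patient's two arms. Section 5.0 says: "Paired t-tests will be used to compare measures averaged to produce a single pre-tourniquet hand volume and a single post-tourniquet hand volume". The mixed model in the same section accounts for within-subject correlation and for "history of ALND, arm position after tourniquet use, and patient-specific risk factors". Section 5.2 adds time, but only for the secondary outcome. The procedural data listed in Section 5.1 B are: "Procedural measures: hand volume and percent change". Arm order appears in none of these places.

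Section 5.3 sets a non-inferiority margin of 1 percentage point and attributes a confidence bound above it to the prior dissection.

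**The concern.** A paired comparison removes differences between patients. It does not remove a systematic difference between the first and the second arm tested unless the order varies across patients. If every ALND arm goes first, the mean paired difference estimates the ALND effect plus the order effect, and no later analysis can separate the two.

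The direction matters. If the swelling response falls from first to second arm, the ALND arm looks worse and the trial loses power. If it rises, a real ALND effect is hidden and a false claim of non-inferiority becomes more likely. The margin is 1 point against a pilot median swelling of 9.1%, so a small order effect is enough to matter.

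**Working it through.** **Inputs from Section 5.3.** SD 1.6 points, margin 1 point, true difference 0, N = 45, 40 and 35, stated power 90%, 87% and 82%.

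**Reproducing the stated power.** Take a paired t-test with uncorrelated arms, so SD of the difference = 1.6 × √2 = 2.263. Non-inferiority is declared when the upper bound is below 1. Power = P(T > t₁₋α) with T noncentral t, N − 1 df and noncentrality 1/(2.263/√N). One-sided 5% gives 89.9%, 86.5% and 82.0%, within 0.6 points of the stated values. One-sided 2.5% gives 82.6%, 77.8% and 71.9%, which does not match. One-sided 5% is therefore used below.

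**Identifiability.** With every ALND arm first, the design matrix with columns for intercept, ALND arm and first arm has rank 2 out of 3. With both orders present it has rank 3. An order term therefore cannot be fitted under a fixed order.

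**Effect on the primary test.** Let b be the mean percent change in the first arm minus that in the second, for reasons other than ALND. The expected paired difference is δ + b, where δ is the ALND effect. The documents give no value for b, so 0.1, 0.25 and 0.5 points are assumptions.

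- Power at δ = 0 with b positive: noncentrality (1 − b)/SE.
- False non-inferiority at δ = 1 with b negative: noncentrality |b|/SE.
- SE at N = 45: 2.263/√45 = 0.337.

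| Size of b (points) | Power, SD 2.26 | Error, SD 2.26 | Power, SD 1.60 | Error, SD 1.60 |
|---|---|---|---|---|
| 0 | 89.9% | 5.0% | 99.3% | 5.0% |
| 0.1 | 83.7% | 8.8% | 98.1% | 10.9% |
| 0.25 | 70.7% | 18.0% | 92.7% | 27.0% |
| 0.5 | 42.6% | 42.6% | 66.2% | 66.2% |

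SD 1.60 is included because Section 5.0 averages repeated measures. With two averaged runs and uncorrelated arms, SD of the difference = √(2 × 1.6² × (1 − f/2)), where f is the run-to-run share of the variance. This runs from 2.26 (f = 0) to 1.60 (f = 1).

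The bias that doubles the 5% error is 0.124 points at SD 2.26 (0.124/9.1 = 1.4% of the pilot swelling) and 0.088 points at SD 1.60. At one-sided 2.5% and SD 2.26 the pattern is the same: power 82.6%, 74.2%, 58.5% and 30.5%; error 2.5%, 4.7%, 10.8% and 30.5%.

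**Could the two cuff cycles per arm reveal drift?** Number the runs 1–2 on the ALND arm and 3–4 on the control arm. A drift of d per run biases the ALND difference by 2d. The within-arm estimate of d has SE = run SD/√45. Two-sided 5% power:

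| Assumed run SD | SE | Bias 2d = 0.25 | Bias 2d = 0.5 |
|---|---|---|---|
| 1.0 | 0.149 | 13.0% | 37.5% |
| 0.5 | 0.075 | 37.5% | 90.7% |

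A step change between arms stays wholly in the ALND estimate, with or without a linear run trend, and fitting the trend multiplies the variance of that estimate by 5.

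**With balanced order.** The paired difference has mean δ + b in one order group and δ − b in the other, so the average of the two group means is δ. With a 23/22 split, SE = ½ × 2.263 × √(1/23 + 1/22) = 0.337 on 43 df. Power is 89.83%, against 89.86% without the order term.

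**The case against.** - **Section 4.0 may be only a narrative.** It describes one arm and says the other is done likewise; it never states that the ALND arm must go first. This is true. But ALND-first is the natural reading and no section gives another order. If staff may choose, the choice is neither governed by a rule nor listed for recording, so balance could not be checked.
- **No order effect is shown and no mechanism is offered.** This stands. Each arm is referred to its own baseline after elevation, which removes drift in resting volume. It does not remove a change in swelling response or in the post-cuff measurement. Section 2.0 reports that in the pilot "40 mmHg was identified as leading to repeatable swelling without acute or chronic abnormalities", but this was in healthy volunteers and does not say whether it held across arms or within a session.
- **The magnitudes are assumed.** They are. They show how sensitive the 1-point test is, not how likely an order effect is.
- **The within-arm check is not always weak.** At run SD 0.5 it has 90.7% power for a 0.5-point bias. Also, SD 2.26 implies no run-to-run variance, whereas run SD 1.0 would give about 2.03, so the two illustrations do not share one set of assumptions. The check still cannot see a step between arms, and each arm's second cycle follows a cuff on that same arm.
- **Once order is balanced, the planned paired t-test suffices.** Nearly so: with a 23/22 split and a 0.5-point order effect it has error 4.3–4.9% and power 88.5–89.7%, depending on direction. Adjustment does no worse (89.8%) and guards against imbalance if uninformative patients fall unevenly between orders.
- **The safety aim and complication data do not depend on this contrast.** Correct; the point concerns the primary volume comparison only.

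**Conclusion.** The concern holds. If Section 4.0 is followed as written, arm order and ALND side cannot be separated, and Section 5.3's attribution of an exceeded margin to the dissection is not supported by the design. That follows from the structure alone. How much it matters depends on an order effect whose existence, size and sign the documents do not give. Across the assumed 0.1 to 0.5 points and SDs of 1.60 to 2.26, the false non-inferiority rate goes from 5% to between 9% and 66%, or, with the opposite sign, power falls by between about 1 and 47 percentage points. This should be fixed before testing begins, because no analysis can repair it afterwards. Confidence is medium, since the text does not expressly require ALND-first and no order effect has been demonstrated.

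**What to change.** - **Section 4.0:** randomise in blocks, or alternate 1:1, which arm is tested first. If either arm may already go first, state the rule.
- **Section 5.1 B:** add arm order to the procedural measures.
- **Sections 5.0 and 5.2:** state in advance that the ipsilateral-minus-contralateral difference, adjusted for arm order as a fixed effect, decides non-inferiority against the 1-point margin. Keep the unadjusted paired t-test as supportive.
- **If the order must stay fixed:** state that the ALND effect cannot be separated from arm order, and report run 1 against run 2 within each arm only as a limited check on gradual drift.

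The cost is an allocation list, one recorded field and one degree of freedom. The procedures on each arm are unchanged, and no extra patients or visits are needed.
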